6.4 Sample Size and Power

For the RCT, we followed established rules of thumb for pilot trial size estimation for two-armed studies to determine our total sample size of 100 (Whitehead et al., 2016). Even accounting for greater than 15% attrition, power analyses (Faul et al., 2009) indicate that this sample size will produce 80% power to detect a large effect for group differences between conditions over time ($f = .72$). This pilot trial is not intended to detect statistically significant differences in outcomes; rather, the primary aim of this pilot is to establish the feasibility of research procedures in preparation for a fully-powered RCT. The effect sizes obtained in this pilot study will be used to estimate parameters for a subsequent R01 to inform sample size considerations.

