3 INVESTIGATIONAL PLAN

3.1 General Schema of Study Design

The study utilizes a mixed methods design which involves a qualitative phase and randomized trial phase. The qualitative phase consists of two steps: 1) interviews with 15 youth and 15 caregivers and 2) field testing of the intervention with 5 youth and 5 caregivers. The qualitative phase and field testing will occur prior to the randomized trial. The randomized trial is a prospective design comparing adapted STAT-ED with comparison condition. We will test the adapted patient navigation intervention in a small RCT with 50 Black youth presenting in the ED with suicidal ideation or behaviors and their caregivers. The RCT will be conducted after an amendment to the study is approved by the IRB. Medical and mental health information will be collected from medical records.

Caregiver and youth interviews will be conducted separately and virtually either over the telephone or through a CHOP approved virtual meeting platform, either Blue Jeans or Microsoft Teams. Interviews will be recorded. We will incorporate feedback from the youth and caregiver qualitative interviews as well as elicit feedback on which intervention components will be adapted and the types of cultural adaptations needed from the study Advisory Group (caregivers, youth, and clinicians) and a consultant.

During the field testing, we will conduct as rapid-cycling prototyping and testing to gather information on intervention content, materials, and delivery. This will involve conducting the intervention, examining recruitment strategies and gaining more information about mental health referral strategies.

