RCT: Study staff will contact enrolled participants, complete baseline assessments, and randomize to the adapted STAT-ED or control condition (enhanced Treatment as Usual). The adapted STAT-ED will involve the following strategies: psychoeducation, motivational interviewing, problem solving logistical barriers, and assistance with making and following up with mental health appointments. This could involve identifying additional mental health resources and providers based on insurance type. One social worker has been hired and trained to implement the adapted STAT-ED and the control condition (enhanced Treatment as Usual) for study. Patient navigator will communicate with the family in person, by telephone, and/or by text messaging via family's preference. The control condition (enhanced Treatment as Usual) will receive telephone contacts to check in and remind families about mental health care initiation. Telephone contacts are consistent with current ED practice in which social work team members follow up by telephone with patients and their caregivers about referrals given at ED discharge. The proposed study is a small pilot to adapt a patient navigator intervention for suicidal Black youth and test the preliminary effectiveness of the intervention in preparation for a fully-powered RCT. We will perform initial analyses (chi-square and *t*-tests) to compare the intervention and control groups on proportion to initiate mental health treatment, mean number of days to treatment initiation, and mean number of treatment sessions at both 2 months and 6 months follow-up. A Cox proportional hazards model will examine group differences in mental health utilization, time to treatment initiation, suicidal ideation, and mental health motivation (Cox, 1972). Assessments may be conducted in-person, via telephone, or electronically/online. At the end of the study, we will also solicit and review feedback from the patient navigator who is research staff member about feasibility and acceptability. The patient navigator will also complete fidelity measure after first session of the adapted STAT-ED.

Participants may be recontacted to update information or to see if they are interested in participating in other research.

3.2 Allocation to Treatment Groups and Blinding.

In the RCT, subjects will be randomized to either the adapted STAT-ED or to enhanced treatment as usual. Randomization will be accomplished in advance using computer-

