3.3.2 Total Number of Study Sites/Total Number of Subjects Projected

The study will be conducted at approximately 1 investigative site at CHOP in the United States.

Recruitment for RCT will stop when approximately 100 participants (50 youth-caregiver dyads) are enrolled. It is expected that approximately 100 subjects will be enrolled to produce 85 evaluable subjects. Recruitment for interviews will stop when approximately 30 participants (15 youth-caregiver dyads) are enrolled and recruitment for field testing will stop when approximately 10 (5youth-caregiver dyads) are enrolled.

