5.2 Efficacy Evaluations

In the RCT, these are the measures that will be used to assess efficacy (mental health utilization)- ED STARS. The three primary efficacy outcomes are 1) whether the patient initiated mental health treatment (yes/no), 2) time to treatment initiation, and 3) number of

treatment sessions attended. Other outcomes are suicidal ideation and behavior measured by SIQ-Jr.

5.2.1 Diagnostic Tests, Scales, Measures, etc.

In the qualitative interviews, the research staff will conduct semi-structured interviews with questions concerning perceptions and preferences of mental health treatment and barriers and facilitators to accessing mental health services with youth and caregiver participants. In the field testing, participants will not complete any measures or scales. . In the RCT, ED STARS is an interview and will be administered by research staff to caregivers at 2 (Study visit 2) and 6 months (final visit) after baseline assessment. SIQ-Jr is a self-report measure that will be administered to youth at baseline and 2 and 6 months after baseline assessments.

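### Section 6.4 states 80% power at f = .72, but with about 42 evaluable youth that effect has about 99.5% power as labelled, and 80% is reached at f = .44

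*Combined protocol and SAP*

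**What the plan says.** Section 6.4 says that pilot-trial rules of thumb for two-armed studies were used "to determine our total sample size of 100". It then allows for attrition above 15% and, citing a power program, says that "this sample size will produce 80% power to detect a large effect for group differences between conditions over time ($f = .72"). The next sentence limits the claim: "This pilot trial is not intended to detect statistically significant differences in outcomes". The section closes by saying that the effect sizes obtained will inform the sample size of the next trial.

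The unit behind the 100 is given elsewhere. Section 3.3.2: "Recruitment for RCT will stop when approximately 100 participants (50 youth-caregiver dyads) are enrolled", and "It is expected that approximately 100 subjects will be enrolled to produce 85 evaluable subjects". Section 3.1: "We will test the adapted patient navigation intervention in a small RCT with 50 Black youth presenting in the ED". The three primary efficacy outcomes in section 6.1 (initiation yes/no, time to initiation, number of sessions) each have one value per youth.

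For these outcomes section 3.1.2 plans chi-square tests, t-tests and a Cox model, comparing the proportion initiating, "mean number of days to treatment initiation, and mean number of treatment sessions at both 2 months and 6 months follow-up". On the source instrument, section 5.2.1 says "ED STARS is an interview and will be administered by research staff to caregivers at 2 (Study visit 2) and 6 months (final visit"). Section 6.4 names no outcome, test, alpha, sidedness, allocation ratio, number of measurements or correlation for its power figure.

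**The concern.** For two equal groups, f = d/2, so f = .72 is d = 1.44. That is a very large effect for a sample of this size to need for 80% power. Either the power is understated, or the metric is not Cohen's f, or the calculation refers to an analysis that the section does not describe.

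This is the RCT's only quantitative statement of sensitivity. A reader will take .72 as the smallest standardised effect that the pilot can detect with 80% power, and as labelled that is wrong by a wide margin. If d was meant, the direction reverses for the planned t-tests, which would have less than 80%. The text does not let the reader tell which applies. The phrase about differences over time adds to the doubt: it points to a repeated-measures test, but none is planned for the primary outcomes. Elsewhere in section 6 that phrase is used only for the SIQ-Jr total score (6.3.2), which is not a primary outcome.

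**Working it through.** **Inputs.** From the documents: f = .72 and 80% power (6.4); 50 randomised youth (3.1, 3.3.2); 85 evaluable of 100 persons (3.3.2), so 85/2 = 50 × .85 = 42.5, about 42 youth; two arms (6.4). Assumed because not stated: two-sided alpha .05 and 1:1 allocation.

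**Step 1: try to reproduce the 80%.** Two-group F test, df 1 and N − 2, noncentrality λ = N f². At N = 42, λ = 42 × .72² = 42 × .5184 = 21.8.

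| N | Power at f = .72 | f for 80% power |
|---|---|---|
| 17 | 79.2% | .727 |
| 18 | 81.8% | .703 |
| 42 | 99.5% | .443 |
| 50 | 99.9% | .404 |
| 85 or 100 | over 99.99% | .307 (at 85) |

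The printed 80% is not reproduced. At N = 42, 80% is reached at f = .443, that is d = 2 × .443 = .886, about .89. Counting persons instead of youth (85 or 100) moves further from 80%. Attrition of 20% to 30% (40 to 35 youth) raises the detectable f only to .455 to .488.

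**Step 2: stricter alpha, N = 42, f = .72.** Power is 98.2% at .0167, 97.1% at .01 and 85.5% at .001.

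**Step 3: repeated measures, N = 42, alpha .05, m = 2 or 3 assessments, correlation ρ from 0 to .99.**
- Between-group effect, λ = N f² m / (1 + (m − 1)ρ): f for 80% power is .313 to .442 (m = 2) and .256 to .442 (m = 3).
- Univariate group-by-time, λ = N f² m / (1 − ρ): .031 to .313 (m = 2) and .028 to .282 (m = 3).
- Multivariate group-by-time, m = 3, df 2 and 39: about .50 with λ = 42 f² and .52 with λ = 39 f². Power at f = .72 is still about 98%.

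None of these needs an f near .72.

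**Step 4: what would give 80% at f = .72.** An analysis of about 17 or 18 youth in total. Section 6.4 describes none.

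**Step 5: read .72 as Cohen's d, so f = .36.**
- Two-sided t-test: 62.4% at 42 and 70.3% at 50.
- Between-group effect, three assessments, ρ = .5: λ = .36² × 42 × 3/2 = 8.16, power 79.6% (80.6% at 43).
- Between-group effect, two assessments, ρ = .3: λ = .36² × 42 × 2/1.3 = 8.37, power 80.6%.
- One-sided t-test at 50 with no attrition: 80.6%.

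The last three set-ups each give about 80% but are mutually incompatible, and the protocol states none of them.

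**The case against.** The strongest reply is that the sentence is merely under-specified. With no test, alpha or outcome stated, it cannot be shown to be wrong, and some set-up may yield .72. One planned comparison comes close. Mean days to initiation is observed only in youth who start treatment. If 6 of 21 and 11 of 21 did so (assumed rates near 30% and 50%), 80% power would need d = 1.52, which for a 6/11 split is f = 1.52 × √(6 × 11)/17 = .73. This is fair as far as it goes, but those rates appear nowhere in the documents, and 6.4 mentions neither initiators nor that outcome; its reference to change over time does not fit it. Under-specification explains why the source cannot be traced. It does not remove the mismatch between the figure as labelled and the sample that 6.4 and 3.3.2 describe.

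The second reply is that this is a pilot: significance is disclaimed, the size came from rules of thumb, and no enrolment target, visit or decision rule depends on the sentence. All of that stands, and it limits the impact. Taken literally as f, the error also runs in the conservative direction.

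A reader might infer more than the documents support:
- *The sample size is wrong, or the trial needs more youth.* Nothing here shows that, because the size was not derived from this power figure.
- *The authors printed a d as an f.* This is possible, but several incompatible set-ups fit equally well, so it is not established.
- *Persons were counted as independent units.* At 85 or 100, f = .72 has over 99.99% power, and .72 read as d in a two-sided t-test has 90.7% at 85 and 94.6% at 100. Neither explains 80%.

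**Conclusion.** The point holds, with limited impact. As labelled, 80% power at f = .72 does not match about 42 evaluable youth: power is about 99.5%, and 80% is reached at f = .44 (d = .89). These figures rest on two-sided .05 and 1:1 allocation, neither of which is stated. The mismatch persists at an alpha as strict as .001 and under the repeated-measures forms tried, where the detectable f is about .44 or less in the univariate tests and about .50 to .52 in the multivariate one. What .72 represents cannot be determined from the documents. The conclusion is that the claim is not reproducible as labelled and should be corrected. It is not a finding that the trial is too small.

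**What to change.** Restate 6.4 in youth: 50 randomised, about 42 evaluable. The authors should first confirm the allocation ratio, because both options below depend on it.

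(a) Replace the power sentence with one that names outcome, test, alpha, sidedness and effect-size metric and, if repeated measures were meant, the number of assessments and the correlation. For example: *With about 42 evaluable youth, 1:1 allocation and a two-sided t-test at .05, there is 80% power for d = .89 (f = .44) in mean number of sessions at one time point.* This figure must not be applied to mean days to initiation, which only initiators supply.

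(b) Or delete the power sentence and state expected precision with its assumptions. At 21 per arm, the approximate (Wald) 95% half-width for the risk difference in treatment initiation is 1.96 × √(p₁(1 − p₁)/21 + p₂(1 − p₂)/21). That is 24 points if both rates are 20% and 30 points if both are 50%. The rates are illustrative, and the Wald form is rough at 20%, with about four events per arm.

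The cost is a wording change in 6.4. Enrolment, visits and analyses are unaffected. The one downside is that the printed 80% power at f = .72 is replaced or removed.

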7 SAFETY MANAGEMENT

7.1 Clinical Adverse Events

Clinical adverse events (AEs) will be monitored throughout the study.

7.2 Adverse Event Reporting

Since the study procedures are not greater than minimal risk, SAEs are not expected. If any unanticipated problems related to the research involving risks to subjects or others happen during the course of this study (including SAEs) they will be reported to the IRB in accordance with CHOP IRB SOP 408: Unanticipated Problems Involving Risks to Subjects. AEs that do not meet prompt reporting requirements will be summarized in narrative or other format and submitted to the IRB at the time of continuing review (if continuing reviews are required), or will be tracked and documented internally by the study team but not submitted to the IRB (if continuing reviews are not required).

8 STUDY ADMINISTRATION

8.1 Treatment Assignment Methods

8.1.1 Randomization

Randomization will be accomplished in advance using computer-generated random numbers. Allocation concealment (blinding of the treatment assignment) will be implemented using sealed, opaque envelopes.

8.1.2 Blinding

Allocation concealment (blinding of the treatment assignment) will be implemented using sealed, opaque envelopes to prevent staff and participants from manipulating the randomization.

8.2 Data Collection and Management

All records generated during this study will be kept confidential in accordance with Institutional policies and HIPAA on subject privacy. All data for these study procedures will be maintained on CHOP/Penn/NIH secure servers, and all analyses will be performed on de-identified data only. All collected study measures will be entered directly into a REDCap database maintained and protected on this secure research server. Any paper copies of research instruments will be kept in locked file cabinets at CHOP. Recordings of interviews will be stored on a password protected secured servers at CHOP/Penn to be coded and analyzed. All audio files will be sent to ADA Transcription services for transcription with deletion of any identifying information. The de-identified transcripts will be returned and maintained on CHOP's secure research server with regular backup. The ADA Transcription services is a CHOP approved vendor that have been used before for other research studies at CHOP and will continue to be used in the future. A master list, linking the study data with subject PHI will be stored separately from the data in a password-protected file on a secure CHOP drive accessible only to the study team. Participants' information will be stored in the REDCap database and configured to export data without PHI. The coded data may be shared with the study sponsor, University of Pennsylvania, other other research staff at CHOP/Penn for current or future research purposes. Every 6 months, the study sponsor NIMH requires a data transfer to the NIMH Data Archive (NDA). During the course of the study and after its completion, the research team will send coded data to the NDA repository where it will be stored and managed. Additionally, any necessary study data will be transmitted accordingly to Clinicaltrials.gov. Identifiable and non-identifiable information may be stored for future research purposes indefinitely.

8.3 Confidentiality

All data and records generated during this study will be kept confidential and in accordance with institutional policies and HIPAA on subject privacy. Participation in all aspects of the proposed study is completely voluntary. The research team will institute strict procedures to maintain confidentiality. Subjects will be assigned a unique identification code that will be

used as the sole identifier whenever possible. Any results obtained cannot be related to the original source, so no results would be provided to the patient, healthcare provider, or insurance provider. Per standard NIH guidelines, a Certificate of Confidentiality will be automatically generated for this NIH-funded study. No identifiable data will be used for future study without first obtaining IRB approval or determination of exemption. The investigator will obtain a data use agreement between the provider (the PI) of the data and any recipient researchers before sharing a limited dataset.

8.4 Regulatory and Ethical Considerations

8.4.1 Data and Safety Monitoring Plan

The CHOP PI will monitor and review the study progress, subject safety, and the accuracy and security of the emerging data. In accordance with the NIH requirements, we will adopt a Data and Safety Monitoring Plan. All SAEs will be reported to the IRBs in accordance with CHOP and Penn IRB policies. AEs that are not serious will be summarized in narrative or other format and submitted to the CHOP and Penn IRBs the University of Pennsylvania, to the OHRP and to the NIMH Project Officer at the time of continuing review. We will use the centralized Data Safety Monitoring Board (DSMB) that was developed for the Center. The DSMB will meet regularly to review the study progress, review modifications, and monitor compliance with IRB rules, human subjects' procedures, OHRP regulations, and plan for rules for stopping clinical trial. This project will be under the Penn Inspire DSMB. Its members and their credentials will be submitted to the University of Pennsylvania IRB and to NIMH prior to any Project accruing human research participants. The DSMB will comprise at least four members with expertise in clinical psychiatry, mental health services research, biostatistics, and bioethics. The DSMB will hold scheduled annual meetings in person or virtually to review any INSPIRE Project or Pilot Study involving a clinical trial by NIH criteria. These will be supplemented by *ad hoc* interim meetings on a particular project(s) during the year, as needed. The DSMB will review and approve the research protocol and examine progress annually.

8.4.2 Risk Assessment

The study procedure risks are not greater than minimal. The research involves the collection of sensitive and protected health information from participants. The risk of participation is considered minimal. There is a potential risk of breach of confidentiality of information and study results about individuals. This risk is minimized by measures taken by the study team to ensure confidentiality: use of secure files, storing data on secure computers, using unique study identifiers, using only coded data for analysis, and obtaining a Certificate of Confidentiality through NIH. A second risk is that participants may become uncomfortable in completing study measures. The risks to participants of the measures and intervention are similar to those associated with receiving care coordinating services for mental health treatment referral. The discussion of personal and sensitive material (e.g., mental health) may make participants uncomfortable. The participants' right to refuse to answer questions or discontinue a procedure will be communicated to them and respected and considered to be an essential component of maintaining a positive study experience for the participant.

Some further potential risks to participants include disclosing child abuse/neglect, suicidal ideation and behaviors, and homicidal ideation. Additionally, the family's routine activities may be disrupted slightly because of participation in the study. Participants will not be deceived in any way about the nature of the study or reimbursement. Suicidal ideation and behavior are risk factors for suicide attempt or death. Therefore, there is increased risk of suicide among the participants regardless of their participation in the study.

Should suicidal ideation or behaviors or functioning worsen, we will implement a suicide prevention plan to assess immediate risk for harm. Participant will be assessed for suicidal risk and determine next steps, such as contacting provider, revising safety plan and/or referral to Emergency Department at a nearby hospital for evaluation for psychiatric hospitalization. Should child maltreatment be suspected, study staff will comply with all mandated reporting laws.

8.4.3 Potential Benefits of Trial Participation

There are direct benefits to the individuals for study participation for the field testing and randomized trial but not for the interviews. All field testing participants will receive the intervention. For RCT, youth assigned to the intervention arm will receive patient navigation services to potentially reduce barriers to receiving mental health treatment. Additionally, the youth in the control condition (enhanced Treatment as Usual) will receive telephone contacts which may benefit their receipt of mental health treatment. There are benefits to society for increasing the understanding of motivation for obtaining mental health treatment and providing more culturally informed care, which may help to increase service utilization among the underserved population of Black youth at risk for suicide.

